2.2 Secondary estimands

Not applicable

3 Study design

[figure not shown]
This is a two cohort, multicenter, open-label, prospective study of 20 RMS patients per treatment arm (optional increase to 30 depending on results of interim analysis) willing to start ofatumumab treatment and receive SARS-CoV-2 modRNA vaccination (initial vaccination or booster vaccine) as part of clinical routine.

- The first cohort will be RMS patients receiving modRNA vaccine as part of clinical routine prior to starting ofatumumab treatment.
 - Cohort 1a will receive their initial SARS-CoV-2 mRNA vaccines (vaccination 1 and vaccination 2) before starting ofatumumab treatment
 - Cohort 1b will receive a booster vaccination before starting ofatumumab treatment
- The second cohort will be participants receiving modRNA vaccine as part of clinical routine while already stable on ofatumumab treatment for at least 4 weeks (since first dose).
 - Cohort 2a will receive their initial SARS-CoV-2 mRNA vaccines (vaccination 1 and vaccination 2) while being on stable ofatumumab treatment
 - Cohort 2b will receive a booster vaccination while being on stable ofatumumab treatment

Initiation and maintenance of ofatumumab treatment in this study will be performed according to the approved SmPC. Especially for cohort 1, possible effects of the previous MS treatment on vaccination efficacy should be kept in mind when scheduling SARS-CoV-2 vaccination. The interventional part of KYRIOS is limited to the collection of blood samples at specified time-points to analyze development of SARS-CoV-2 specific T-cells and neutralizing antibodies as response to the modRNA vaccination in clinical routine.

Figure 3-1 Study design

Cohort 1a and cohort 2a:

PEP: primary endpoint; Vacc.= vaccination with modRNA vaccine;

Vaccination as part of clinical routine; required number of vaccinations and interval depends on SmPC of respective modRNA vaccines or local regulations provided e.g. by German health authorities.

[figure not shown]
Booster vaccination as part of clinical routine e.g. if suggested by German health authorities and at the physician's discretion.

* Ofatumumab treatment has to be initiated at least 4 weeks before Vacc.1,

** Ofatumumab initiation doses can be omitted if patient already receives ofatumumab at the time of screening

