4.5.1 Blood sample volume

A volume smaller than a typical blood donation is planned to be collected over a period of up to 23 months, from each participant as part of the study. Additional samples may be required for safety monitoring.

Timings of blood sample collection are outlined in the assessment schedule (Table 8-1, 8-2, 8-3 and Table 8-4).

A summary blood log is provided in the laboratory manual. Instructions for sample collection, processing, storage and shipment information are also available in the laboratory manual.

Blood samples will be stored until the end of the study in case measurements need to be repeated or confirmed.

5 Study Population

The study population will consist of 40 female and male RMS patients that are planned to be treated in clinical routine with Ofatumumab as per approved SmPC. There is an optional increase to 60 patients after the interim analyses.

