12.8 Sample size calculation

12.8.1 Primary endpoint(s)

The sample size of 20 participants per arm is selected based on need for early availability of results for the current covid-19 pandemic and the feasibility to recruit sufficient participants. This sample size of 20 subjects will provide estimates of proportion responded with margin of error (half-width of a 95% confidence interval) of 20.1%, 19%, and 17.5% corresponding to response rates of 70%, 75%, and 80%, respectively. Adjusting for 10% drop-out, 22 subjects will be enrolled in each arm. In case of fast recruitment the sponsor is allowed to increase

sample size in each arm by up to 10 additional patients to support the generation of meaningful data in a larger sample size.

13 Ethical considerations and administrative procedures

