1.1 Study design

This is a two cohort, multicenter, open-label, prospective study of 40 patients (optionally up to 60) suffering from relapsing multiple sclerosis (RMS).

- The first cohort will be RMS patients receiving modRNA vaccine as part of clinical routine prior to starting ofatumumab treatment.
Cohort 1a: will receive their 1st and 2nd SARS-CoV-2 vaccines (and an optional booster vaccine)
Cohort 1b: will receive a booster vaccine
- The second cohort will be participants receiving modRNA vaccine as part of clinical routine while already stable on ofatumumab treatment for at least 4 weeks (since first dose).
Cohort 2a: will receive their 1st and 2nd SARS-CoV-2 vaccines (and an optional booster vaccine)
Cohort 2b: will receive a booster vaccine

Ofatumumab treatment initiation and maintenance will be performed as per approved SmPC. SARS-CoV-2 mRNA vaccination will be performed as part of clinical routine.

The first interim analysis is planned when at least five patients per cohort have completed the study visit one week after the second SARS-CoV-2 modRNA vaccination or on September 1st 2021, whichever comes first. The data gathered at this time point will be examined as a preliminary evaluation of proof of concept.

The second interim analysis is planned when at least 10 patients that were vaccinated during stable ofatumumab-treatment have passed the primary endpoint, 1 month after the 2nd vaccination or after booster or on January 10th 2022, whichever comes first. The data gathered at this time point will be examined as a preliminary evaluation of proof of concept for the new study design.

An additional interim analysis is planned after all participants have completed the study visit 1 month after the second SARS-CoV-2 modRNA vaccination or booster vaccination, respectively. The data gathered at this time point will be the basis for the primary endpoint of this study.

Additional interim analyses may be conducted to support decision making concerning the current clinical study including an increase in participants (from 40 to 60), the sponsor's clinical development projects in general, or in case of any safety concerns.

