2.15 Interim analysis

See section 1.1 Study design.

3 Sample size calculation

The sample size of 20 participants per arm is selected based on need for early availability of results for the current covid-19 pandemic and the feasibility to recruit sufficient participants. This sample size of 20 subjects will provide estimates of proportion responded with margin of error (half-width of a 95% confidence interval) of 20.1%, 19%, and 17.5% corresponding to response rates of 70%, 75%, and 80%, respectively. Adjusting for 10% drop-out, 22 subjects will be enrolled in each arm. In case of fast recruitment the sponsor is allowed to increase sample size in each arm by up to 10 additional patients to support the generation of meaningful data in a larger sample size.

4 Change to protocol specified analyses

The efficacy analysis set was defined in such a way that it can be applied to all efficacy analyses. With regard to the primary parameter, there is no change in content compared to the definition in the study protocol.

5 Appendix

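### The study size is given as 40 in some sections and as 22 enrolled per arm (44) in others, with two different triggers for the extension; these should be reconciled and precision restated for the planned exact interval.

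*Protocol*

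**What the plan says.** - **Size, design sections.** Protocol 3 describes "20 RMS patients per treatment arm (optional increase to 30 depending on results of interim analysis". Protocol 5 states: "The study population will consist of 40 female and male RMS patients", with an optional rise to 60 after the interim analyses. The Protocol summary also gives 40, optionally 60. SAP 1.1 has a "prospective study of 40 patients (optionally up to 60".
- **Size, sample-size sections.** Protocol 12.8.1, repeated in SAP 3, starts from 20 per arm: "The sample size of 20 participants per arm is selected based on need for early availability of results", together with feasibility of recruitment. It then states: "Adjusting for 10% drop-out, 22 subjects will be enrolled in each arm".
- **Precision.** The same paragraph gives a "margin of error (half-width of a 95% confidence interval) of 20.1%, 19%, and 17.5" per cent, "corresponding to response rates of 70%, 75%, and 80%, respectively".
- **Extension.** SAP 3 and Protocol 12.8.1 say: "In case of fast recruitment the sponsor is allowed to increase sample size in each arm by up to 10 additional patients". Protocol 4.4 and SAP 1.1 list the increase from 40 to 60 among the decisions that further interim analyses may support.
- **Interval.** Protocol 12.4.2 and SAP 2.5.2 specify an exact Clopper-Pearson 95% interval for the response proportion in each cohort.

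**The concern.** A reader cannot tell from the current text whether 40 is the number to enrol or the number to analyse. If it is the number to enrol, there is no allowance for the plan's own 10% drop-out, and the margins quoted for 20 per arm are slightly too favourable. If it is the number to analyse, no section says so.

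The extension rule has a similar gap. Adding patients after looking at response rates is a different decision from adding them because recruitment is quick. In an open-label, non-randomised study, the report should say which one applied. No test is planned, so neither power nor type I error is at stake. What is affected is the accuracy of the stated precision and the traceability of the sample size in the study report, which is to be written from the SAP's outputs.

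**Working it through.** **Inputs** (Protocol 12.8.1 and SAP 3): n = 20 per arm; response rates p = 0.70, 0.75, 0.80; 95% confidence; 10% drop-out; 22 enrolled per arm. Two arms (Protocol 6.1.3).

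**1. Reproduce the stated margins.** Normal approximation: 1.96 × √(p(1−p)/20) = 20.08, 18.98 and 17.53 points. This matches the stated 20.1, 19 and 17.5. A Wilson interval (18.7, 17.8, 16.8) does not match, and neither does Clopper-Pearson (21.2, 20.2, 19.0).

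**2. Enrolment.** 2 × 22 = 44, against 2 × 20 = 40. The figure 22 is 20 × 1.1. Expected evaluable: 22 × 0.9 = 19.8 per arm.

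**3. Ceiling.** 2 × (20 + 10) = 60, which agrees with the other sections. 2 × (22 + 10) = 64, which is printed nowhere.

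**4. If only 40 were enrolled.** 20 × 0.9 = 18 per arm if every drop-out leaves the denominator, and 20 if none does. Under Protocol 12.4.3 and SAP 2.2, patients in cohorts 1a and 2a who miss the second dose stay in as non-responders. Patients vaccinated but without a valid T-cell result leave the denominator. Protocol 9.1.1.1 replaces patients not vaccinated within three months of screening, with an exception for those not yet eligible under local regulation. The range is therefore 18 to 20.

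**5. Half-widths in percentage points.**

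| Evaluable per arm | Method | 70% | 75% | 80% |
|---|---|---|---|---|
| 20 | Normal approximation (as stated) | 20.1 | 19.0 | 17.5 |
| 19.8 | Normal approximation | 20.2 | 19.1 | 17.6 |
| 18 | Normal approximation | 21.2 | 20.0 | 18.5 |
| 20 | Clopper-Pearson (as planned) | 21.2 | 20.2 | 19.0 |
| 18 | Clopper-Pearson | 22.3 | 21.3 | 20.0 |

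The Clopper-Pearson rows take half the interval length. At 20 the counts are 14, 15 and 16, with intervals 45.7–88.1, 50.9–91.3 and 56.3–94.3%. At 18 the counts n × p are fractional (12.6, 13.5, 14.4), so that row is approximate.

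**6. Size of each effect.** Going from 20 to 18 evaluable on the plan's formula adds 21.17 − 20.08 = 1.1, 20.00 − 18.98 = 1.0 and 18.48 − 17.53 = 0.95 points. Going from the normal approximation to Clopper-Pearson at a full 20 adds 21.19 − 20.08 = 1.1, 20.22 − 18.98 = 1.2 and 18.96 − 17.53 = 1.4 points. The choice of formula costs at least as much as the possible drop-out shortfall.

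**7. Trigger.** Protocol 3 makes the increase depend on interim results, and Protocol 5 places it after the interim analyses. Protocol 12.8.1 and SAP 3 allow it when recruitment is fast and mention no interim result.

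**The case against.** The best defence is that 40 is the target before inflation. Protocol 12.8.1 calls 20 per arm the sample size and then inflates it to 22, and only that paragraph and its copy in SAP 3 give an enrolment figure after drop-out. On this reading the sections agree and the stated precision is in effect delivered. The reading is reasonable, but no section labels 40 that way, and Protocol 5 presents it as the study population. The labelling fault stands.

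Several stronger readings are tempting, and the documents do not support them:

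- **A ceiling of 64.** This requires adding the 10 to 22. The paragraph uses sample size for 20, and 20 + 10 gives the stated 60. The fault is only that the base is not stated.
- **18 evaluable per arm as a fact.** It arises only if 40 are enrolled and every drop-out leaves the denominator.
- **22 as a material error.** 20/0.9 = 22.2 would round up to 23, but 19.8 rather than 20 evaluable changes the margin by about 0.1 point.
- **Precision as the sole basis for the size.** Protocol 12.8.1 gives early results and feasibility as the reasons. Precision is what that size then provides.

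It can also be said that the two triggers may coexist, one informing the decision and the other permitting it. That is possible, but no section says so.

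Finally, the Amendment 3 summary stops recruitment, so no enrolment decision remains, and the actual interval will be reported at the actual number. This lowers the severity. It does not remove the point, since SAP 5.1 cites notes to file from September and October 2023 while SAP 3 still describes enrolment as future.

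**Conclusion.** The contradiction is real and lies in the current text of both documents: 40 against 44, an unstated base for the extension, and two triggers. The consequence for precision is small and conditional. If 40 were enrolled and all drop-outs at the plan's 10% rate left the denominator, the margins would be about 1 percentage point wider than stated. If 22 per arm were enrolled, they are in effect met on the formula used. Separately, even with 20 evaluable, the stated margins are about 1.1 to 1.4 points narrower than the planned Clopper-Pearson interval would give at the assumed response rates. This is a low-severity matter of consistency. It does not threaten the validity of the primary analysis, which is descriptive and has no test.

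**What to change.** 1. Use one labelled set of figures in the Protocol summary, Protocol 3, 4.4, 5 and 12.8.1 and SAP 1.1 and 3. Either give 20 evaluable and 22 enrolled per arm, or give 40 enrolled in total with precision restated at the resulting evaluable number.
2. State that the 10 additional patients per arm are added to 20, so that the ceiling is 60, and label 60 in the same terms as 40.
3. Reconcile the extension trigger to one rule. The documents do not settle which; the sponsor should state the rule that applied.
4. Compute the margins with Clopper-Pearson: about 21.2, 20.2 and 19.0 points at 20 per arm, or about 22.3, 21.3 and 20.0 at 18, for 70, 75 and 80%.
5. In SAP 3, give precision at the number actually enrolled.

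The cost is wording and slightly wider stated margins. No additional patients, data or analyses of trial data are needed.

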13.1 Regulatory and ethical compliance

This clinical study was designed and shall be implemented, executed and reported in accordance with the ICH Harmonized Tripartite Guidelines for Good Clinical Practice, with applicable local regulations (including European Directive 2001/20/EC, US CFR 21), and with the ethical principles laid down in the Declaration of Helsinki.

13.2 Responsibilities of the investigator and IRB/IEC

Before initiating a trial, the investigator/institution must obtain approval/favorable opinion from the Institutional Review Board/Independent Ethics Committee (IRB/IEC) for the trial protocol, written informed consent form, consent form updates, participant recruitment procedures (e.g., advertisements) and any other written information to be provided to participants. Prior to study start, the investigator is required to sign a protocol signature page confirming his/her agreement to conduct the study in accordance with these documents and all of the instructions and procedures found in this protocol and to give access to all relevant data and records to Novartis monitors, auditors, Novartis Quality Assurance representatives, designated agents of Novartis, IRBs/IECs, and regulatory authorities as required. If an inspection of the clinical site is requested by a regulatory authority, the investigator must inform Novartis immediately that this request has been made.

13.3 Publication of study protocol and results

The protocol will be registered in a publicly accessible database such as clinicaltrials.gov and as required in EudraCT. In addition, after study completion (defined as last patient last visit) and finalization of the study report the results of this trial will be submitted for publication and posted in a publicly accessible database of clinical trial results, such as the Novartis clinical trial results website and all required Health Authority websites (e.g. Clinicaltrials.gov, EudraCT etc.).

For details on the Novartis publication policy including authorship criteria, please refer to the Novartis publication policy training materials that were provided to you at the trial investigator meetings.

13.4 Quality Control and Quality Assurance

Novartis maintains a robust Quality Management System (QMS) that includes all activities involved in quality assurance and quality control, to ensure compliance with written Standard Operating Procedures as well as applicable global/local GCP regulations and ICH Guidelines.

Audits of investigator sites, vendors, and Novartis systems are performed by auditors, independent from those involved in conducting, monitoring or performing quality control of the clinical trial. The clinical audit process uses a knowledge/risk based approach.

Audits are conducted to assess GCP compliance with global and local regulatory requirements, protocols and internal SOPs, and are performed according to written Novartis processes.

14 Protocol adherence

This protocol defines the study objectives, the study procedures and the data to be collected on study participants. Additional assessments required to ensure safety of participants should be administered as deemed necessary on a case by case basis. Under no circumstances including incidental collection is an investigator allowed to collect additional data or conduct any additional procedures for any purpose involving any investigational drugs under the protocol, other than the purpose of the study. If despite this interdiction prohibition, data, information, observation would be incidentally collected, the investigator shall immediately disclose it to Novartis and not use it for any purpose other than the study, except for the appropriate monitoring on study participants.

Investigators ascertain they will apply due diligence to avoid protocol deviations. If an investigator feels a protocol deviation would improve the conduct of the study this must be considered a protocol amendment, and unless such an amendment is agreed upon by Novartis and approved by the IRB/IEC and Health Authorities, where required, it cannot be implemented.

1.1 Study design

This is a two cohort, multicenter, open-label, prospective study of 40 patients (optionally up to 60) suffering from relapsing multiple sclerosis (RMS).

- The first cohort will be RMS patients receiving modRNA vaccine as part of clinical routine prior to starting ofatumumab treatment.
Cohort 1a: will receive their 1st and 2nd SARS-CoV-2 vaccines (and an optional booster vaccine)
Cohort 1b: will receive a booster vaccine
- The second cohort will be participants receiving modRNA vaccine as part of clinical routine while already stable on ofatumumab treatment for at least 4 weeks (since first dose).
Cohort 2a: will receive their 1st and 2nd SARS-CoV-2 vaccines (and an optional booster vaccine)
Cohort 2b: will receive a booster vaccine

Ofatumumab treatment initiation and maintenance will be performed as per approved SmPC. SARS-CoV-2 mRNA vaccination will be performed as part of clinical routine.

The first interim analysis is planned when at least five patients per cohort have completed the study visit one week after the second SARS-CoV-2 modRNA vaccination or on September 1st 2021, whichever comes first. The data gathered at this time point will be examined as a preliminary evaluation of proof of concept.

The second interim analysis is planned when at least 10 patients that were vaccinated during stable ofatumumab-treatment have passed the primary endpoint, 1 month after the 2nd vaccination or after booster or on January 10th 2022, whichever comes first. The data gathered at this time point will be examined as a preliminary evaluation of proof of concept for the new study design.

An additional interim analysis is planned after all participants have completed the study visit 1 month after the second SARS-CoV-2 modRNA vaccination or booster vaccination, respectively. The data gathered at this time point will be the basis for the primary endpoint of this study.

Additional interim analyses may be conducted to support decision making concerning the current clinical study including an increase in participants (from 40 to 60), the sponsor's clinical development projects in general, or in case of any safety concerns.

1.2 Study objectives and endpoints

Objective(s)	Endpoint(s)
Primary Objective(s) To estimate the proportion of RMS patients having established SARS-CoV-2-specific T-cells after receiving a modRNA vaccine (initial or booster) either before or after starting ofatumumab treatment.	Endpoint(s) for primary objective(s) Proportion of RMS patients having established SARS-CoV-2-specific T-cells as defined by detection of SARS-CoV-2 reactive T-cells, measured by e.g. enzyme-linked immunosorbent spot (ELIspot) assay from T-cells that were stimulated with SARS-CoV-2 peptide mix, either one month after second dose of vaccine or one month after booster vaccine in participants who received the respective vaccine before or after starting ofatumumab treatment (yes/no)
Secondary Objective(s) To estimate the proportion of RMS patients maintaining for up to 18 months SARS-CoV-2-specific T cells after receiving a modRNA vaccine either before or after starting ofatumumab treatment.	Endpoint(s) for secondary objective(s) Proportion of RMS patients with detectable SARS-CoV-2 reactive T-cells one week, 6 and 18 months after second dose of vaccine or 6 and 12 months after booster vaccine in participants who received the vaccine before or after starting ofatumumab treatment (yes/no)
To estimate the increase in specific T-cells after receiving a modRNA booster vaccine either before or after starting ofatumumab treatment.	Fold change of SARS-CoV-2 specific T-cell levels one week, 1 month, 6 months, 12 months and 18 months after the second dose of vaccine or 1 months, 6 months and 18 months after a booster vaccine compared to the last timepoint before the respective vaccine
To estimate the proportion of RMS patients achieving seroconversion (i.e. having SARS-CoV-2 serum neutralizing antibodies) after receiving a modRNA vaccine either before or after starting ofatumumab treatment.	Proportion of RMS patients achieving seroconversion (i.e. having SARS-CoV-2 serum neutralizing antibodies) after receiving a modRNA vaccine either before or after starting ofatumumab treatment (yes/no)
To estimate the proportion of RMS patients maintaining for up to 18 months quantifiable levels of SARS-CoV-2 serum functional antibodies after receiving a modRNA vaccine either before or after starting ofatumumab treatment.	Proportion of RMS patients with quantifiable levels of SARS-CoV-2 serum functional antibodies one week, 1, 6, 12, and 18 months after receiving the second dose of modRNA vaccine or 1, 6, and 12 months after a booster shot either before or after starting ofatumumab treatment (yes/no)

Describing phenotypically the cellular response after receiving a modRNA vaccine either before or after starting ofatumumab treatment.

- Phenotypical characterization of peripheral blood mononuclear cells for CD45, CD3, CD4, CD8, CD62l, CD45RA, CD27, CCR7
- Immunophenotyping for naive, central memory, effector memory, and effector cells on CD4+ and CD8+ cells
- Measuring cells positive for intracellular cytokine-staining for interferon-gamma and interleukin-4

Describing safety and tolerability, incl. AEs, SAEs, incl. patients with clinical confirmed patients developing coronavirus disease COVID-19 2019 (COVID-19)

2 Statistical methods

